### Gait evaluation after gait training

After twelve 2 hour sessions of gait practice with cyclical vibration emulating normal muscle activity of lower extremities, baseline speed and distance trials and VICON gait assessment with and without vibration will be repeated to test hypotheses. The primary outcome measures for testing hypotheses will be walking speed and foot-to-floor clearance as measured by vertical

Vibratory stimulation system with inserts showing size and mounting of vibrators over TFL- tensor fasciae latae, RF- rectus femoris, BF- biceps femoris, and TA- tibialis anterior (VSCU-Vibratory Stimulation Control Unit).

displacement of marker placed over the first metatarsal. Force sensing resistors (FSRs) will be used to detect any toe dragging as a result of insufficient foot clearance. Secondary measures will be peak hip, knee and ankle flexion during swing, hip-knee coordination changes, knee flexion during stance and in pre-swing and step length symmetry.

**14. Will the research involve the following?**

N/A **Chart/Data Review**

**Placebo Group**  No  Yes (*describe*):

**Other Control Group**  No  Yes (*describe*): Will be individuals with gait deficits from MS who will undergo the same gait training as treatment group but without cyclical vibration as described under #13 "research design and all study related procedures".

**Randomization**  No  Yes (*describe*): Subjects will be randomly assigned to either treatment or control group using a coin toss.

**Deception**  No  Yes (*describe*):

**15. Does the research involve the use and/or disclosure of Individually Identifiable Health Information in any form or medium?**

No  Yes **If yes, complete the required HIPAA Waiver/Authorization forms.**

**16. Does the study include the administration of a study agent that does not require FDA approval and does not require an IND (e.g. vitamins, food supplements, isotope tracers, alternative medicines, etc.)?**

No  Yes *-provide a detailed description of the procedures used to assure patient safety:*

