#### 10. Describe the means of analyzing the data and evaluating the results.

- *State the anticipated methods to be used for analysis and interpretation of the data.*
- *The methods must compliment the design of the study and the nature of the data which is being collected.*

Primary outcome measures for testing hypotheses will be walking speed measured during 10m walk trials and foot-to-floor clearance as measured by vertical displacement of marker placed over the first metatarsal using our 16-camera VICON motion analysis system. Force sensing resistors (FSRs) will be used to detect any toe dragging as a result of insufficient foot clearance. Secondary measures will be peak hip, knee and ankle flexion during swing, hip-knee coordination changes, knee flexion during stance and in pre-swing, step length symmetry and 6min walking distance.

The within subject experimental design will be used because it requires fewer subjects with more statistical power while reducing the potential for systemic error or selection bias to test the effect of CV on walking. While practice and carryover effects are major disadvantages of this study design, proper precautions including rest periods between tests and randomization of testing order for treatment group will be instituted to minimize them†. In addition to comparison between treatment and control groups, subjects receiving CV can also serve as their own controls by first comparing volitional gait at baseline (VGB) with any gait correction with the CV approximating desired normal muscle activity (CVN). Next the volitional gait *post*- 12 sessions of training with vibration (VGP) will be compared to volitional gait at baseline (VGB). Thus, any improvements at baseline with CVN compared to volitional gait (VGB) can be attributed to short term effects of vibration. Improvements in volitional gait *post* training with vibration (VGP) compared to baseline gait (VGB) will be attributed to long term effects of vibration. The control group subjects will be evaluated at baseline (VGB) and after gait training (VGP) and compared to the intervention group to identify trends and further explore the potential effects of CV. While this study design has limited generalizability due to the inhomogeneity of the selected population, it can be quite useful for developing and refining CV intervention.

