A one-way repeated measures ANOVA will be used to test for significant difference between means to test Hypotheses 1 and 2. The Tukey honestly significant difference multiple comparison test will be used between each pair of mean walking speeds, foot-to-floor clearance and maximum joint angles to determine 95% ( $p < 0.05$ ) confidence intervals for

statistically significant differences between conditions (CVN-VGB, CVN-VGP, VGP-VGB) and between groups to identify trends across all subjects.

† Greenwald AG. With-in subject design: to use or not to use? *Psychological Bulletin*, 83(2):314-320, 1976.

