**11. Provide a BRIEF DESCRIPTION of how the estimated number of study subjects needed for this research was determined**

- *If this is a quantitative study provide the method of determining sample size estimates.*
- *If multiple studies are planned provide a power analysis or justification for each one.*

A statistical power of 90% was used to determine the number of trials with VICON motion analysis system required for the testing and comparison of temporal and spatial gait parameters. The results indicated a requirement of 30 strides of data or roughly 6 trials (approximately 5 strides per trial) for each condition (volitional or CV). Because this is a two year feasibility study to determine the effect size a small sample of 6 subjects were chosen for intervention with six controls to obtain preliminary data for calculating statistical power for the number of subjects required in a larger study to determine the effect of vibration on improving gait in MS.

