**Recruitment and baseline evaluation**

Potential subjects will be identified via chart review or through referral and asked if they would be willing to participate in the study. If agreeing, they would undergo the consent process. Twelve subjects with gait disorders from MS will be recruited for participation in this study, with six subjects assigned to undergo CV gait training and six to control group for gait training without vibration. Subjects will be randomly assigned to either treatment or control group and matched by functional walking category based on speed for data analysis†. After signing the consent form agreeing to participate in the study and meeting inclusion/exclusion criteria, subjects will undergo baseline evaluation. This will include walking speed and distance and using VICON system for temporal and spatial parameters, kinematics and kinetics of gait and EMG activity during volitional gait at their preferred walking speed.

Retro-reflective markers will be placed on the bony landmarks and surface EMG electrodes over target muscles while the subject walks along the 10m walkway instrumented with force platforms. Standard analysis software provided with VICON system will be used to track markers in 3D and calculate all gait parameters so they can be correlated with muscle activity. The baseline evaluation will be done with and without vibration on treatment group and without vibration on control group. Data will be collected during 6 walking trials of at least 5 steps per trial (approximately 30 steps) within the visual field of the VICON motion analysis system under each condition. Sufficient resting time will be provided between trials to complete the assessment. Subjects will be encouraged to use their walking aid while a trained physical therapist provides standby guard during walking for their safety.

[figure not shown]

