### Gait training

Each group will undergo twelve 2 hour sessions of standard gait training (up to 3x/week based on availability). Both groups will receive the same gait training while the treatment group will receive gait training with CV and control group without it.

Up to four vibrators per leg powered by the vibration stimulation control unit (VSCU) will be strapped or taped over ankle dorsiflexor tibialis anterior (TA), knee extensor and hip flexor rectus femoris (RF), knee flexor short head of biceps femoris (BF) and hip flexor and abductor the lateral portion of tensor fasciae latae muscles (TFL) as shown in figure. The cylindrical vibrators will be used to increase vibration intensity as needed. The CV paradigm resembling normal activity of muscles timed to gait events, as detected by accelerometers taped to the shoes and force sensing resistors placed in the insoles, will be imposed during walking. An average frequency of vibration will be set at 80Hz and as high as 150Hz. Physical therapist will conduct all gait training and encourage maximal voluntary effort during training while providing standby assist and spotting the subjects to ensure safety. During walking, heart rate (HR) will be monitored with the chest strap monitor and receiver watch and recorded before and after each walk. Blood pressure (BP) will be measured before and after each session of CV training and evaluation. In addition, subjects will be asked during each session if they experience any untoward sensation. BP and HR during gait training with vibration will be monitored and compared to baseline values. An increase in BP and HR of >20% and experiencing untoward sensation will be considered significant to reject Hypothesis that CV produces no physiological changes.

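### Six subjects per arm are planned, but the only allocation method given is a coin toss, with nothing said about how it yields six and six or how assignments are concealed

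*Protocol*

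**What the plan says.** Protocol item 13 (Recruitment and baseline evaluation) fixes the split at 12 subjects, "with six subjects assigned to undergo CV gait training and six to control group for gait training without vibration". Item 11 repeats it: "a small sample of 6 subjects were chosen for intervention with six controls to obtain preliminary data for calculating statistical power". The randomization entry in item 14 reads: "Subjects will be randomly assigned to either treatment or control group using a coin toss". Neither document adds a restriction, a prepared list or a concealment step, or says who tosses the coin. The SAP mentions randomizing only the order of testing with and without vibration, and no control group.

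Item 13 also says: "Subjects will be randomly assigned to either treatment or control group and matched by functional walking category based on speed for data analysis". It gives no matching ratio and no number of subjects per category.

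On the use of the control arm, item 10 states: "The control group subjects will be evaluated at baseline (VGB) and after gait training (VGP) and compared to the intervention group to identify trends". The training section adds: "Both groups will receive the same gait training while the treatment group will receive gait training with CV and control group without it". Item 20 counts completers: up to 48 subjects are screened so that 12 complete.

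**The concern.** The stated method does not by itself deliver the stated split. If the tosses are free, six and six is left to chance. If tossing stops once an arm is full, the split is met, but the remaining assignments are known to anyone who has counted. Counting would be easy, because arm is visible during training. A physical therapist conducts all the training and a physical therapist also assesses functional eligibility (item 31); the documents do not say whether this is the same person.

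The comparison at stake is between groups. Both arms get the same twelve training sessions, so the change from baseline to post-training volitional gait within the treated arm mixes training with vibration, although item 10 attributes it to long-term effects of vibration. Only the control arm can separate the two, and item 11 wants the data from these 12 people for sizing a larger study. Foreseeable assignments can bias that comparison. Matching by walking category can also leave some subjects without a counterpart.

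**Working it through.** **Inputs.** 12 subjects, 6 per arm (items 11 and 13); coin toss (item 14), assumed fair. Category sizes are not given, so a range is assumed in step 4.

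**1. Free tosses.** The number treated is Binomial(12, 0.5).
- 6:6: C(12,6)/2^12 = 924/4096 = 22.6%
- 7:5 either way: 2 × 792/4096 = 38.7%
- 8:4 or worse: 38.8%
- 9:3 or worse: 14.6%

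If tossing continues until 12 complete (item 20) and dropout is unrelated to arm, these figures do not change.

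**2. Tossing until one arm has six, then filling the other.** One arm fills at toss t with probability 2·C(t−1,5)/2^t, for t = 6 to 11. The remaining 12 − t allocations are forced.

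| Forced allocations | 1 | 2 | 3 | 4 | 5 | 6 |
|---|---|---|---|---|---|---|
| Probability | 0.246 | 0.246 | 0.219 | 0.164 | 0.094 | 0.031 |

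The mean is 2.71, and three or more are forced in 50.8% of sequences. For comparison, in a list drawn at random from the 924 orderings of six and six, the assignments that can be worked out by counting average 12/7 = 1.71, with three or more in 18.2%. The avoidable excess is therefore about one allocation (2.71 − 1.71).

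**3. Precision.** Efficiency relative to 6:6 is (1/6 + 1/6)/(1/a + 1/b). For a baseline-adjusted comparison the 95% half-width, in residual SDs, is t(0.975; 9 df) × √(1/a + 1/b). The 9 df are 12 − 3 (intercept, arm, baseline), and chance baseline imbalance is ignored.

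| Split | Efficiency | Half-width (residual SD) |
|---|---|---|
| 6:6 | 1.00 | 1.31 |
| 8:4 | 0.89 | 1.39 |
| 9:3 | 0.75 | 1.51 |

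**4. Subjects without a match in their walking category.** Two definitions are possible because the protocol gives no matching ratio. Under (a), a subject is unmatched only if the whole category falls in one arm. Under (b), matching is 1:1 within category, so the unmatched number in a category is the absolute difference between the arms. Each cell shows free tosses / 6:6 kept. The 6:6 figures assume arrival order is unrelated to category.

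| Assumed category sizes | Some category in one arm only | Expected unmatched (a) | Expected unmatched (b) |
|---|---|---|---|
| 6, 6 | 6% / 0.2% | 0.38 / 0.03 | 3.8 / 2.6 |
| 4, 8 | 13% / 6% | 0.56 / 0.24 | 3.7 / 2.4 |
| 3, 9 | 25% / 18% | 0.79 / 0.55 | 4.0 / 2.7 |
| 4, 4, 4 | 33% / 14% | 1.50 / 0.73 | 4.5 / 3.6 |
| 3, 4, 5 | 38% / 22% | 1.56 / 0.86 | 4.9 / 4.1 |

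The choice of definition matters more than the choice between free tosses and a kept 6:6.

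**The case against.** The strongest reply is that this is a feasibility pilot, that the group comparison is meant only to show trends, and that the short-term contrast (gait with and without vibration at baseline) does not depend on arm sizes. All of that stands, and so does the modest precision loss.

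A reader might infer that the coin leaves only two routes to six and six, chance or forcing. That goes too far. One toss per matched pair also gives exactly 6:6, and walking speed is available from the eligibility 10 m walk (item 31). Tossing until both arms have at least six would also work, with 12 − 2.7 + 2 × 2.7 = 14.7 subjects on average. The documents describe neither route, and item 13 ties matching to data analysis. So the finding is that the route is unstated, not that no sound route exists.

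A reader might also infer that the toss contradicts the matching. It does not, because matching is described as an analysis step.

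Finally, any scheme that ends at exactly 6:6 forces at least the last allocation. A fixed list shortens the predictable tail by about one allocation and does not remove it. It also leaves the chance of a one-arm category where a capped toss leaves it (0.2% to 22% for the assumed sizes). Baseline adjustment, not the list, deals with unmatched subjects.

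**Conclusion.** The concern holds in a limited form. Six per arm is planned and the only method described does not secure it: followed literally with independent tosses, 12 subjects split 6:6 in 22.6% of cases and 8:4 or worse in 38.8%. With a cap, the last 2.7 allocations on average are known in advance, against 1.7 for a random list. These figures assume a fair coin and 12 subjects.

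Foreseeable assignment without concealment and loss of subjects to matching matter more than precision. The expected number unmatched is 0.4 to 1.6 (free) or 0.03 to 0.9 (6:6 kept) if only one-arm categories count, and about 3.7 to 4.9 or 2.4 to 4.1 under 1:1 matching. All of these rest on assumed category sizes.

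The documents do not show that allocation was in fact biased or unequal, and the within-subject short-term contrast is unaffected. The plan should be corrected because the between-group comparison, though exploratory, is the only one that isolates vibration from training.

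**What to change.** **If allocation is still to come.** In item 14, replace the coin toss with one random list of exactly six and six, prepared in advance. It should be held by someone who neither assesses eligibility nor delivers training, and each assignment revealed only after eligibility is confirmed. In item 13, replace matching by walking category with a comparison of the arms on each post-training outcome adjusted for its own baseline value (speed for speed, clearance for clearance); this drops no one for lack of a match. Add that comparison to the SAP, and state there that the ANOVAs of protocol item 10 ("A one-way repeated measures ANOVA will be used to test for significant difference between means to test Hypotheses 1 and 2") and of the SAP (two-way) serve the within-subject contrasts.

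**If allocation is complete**, as the SAP's past tense suggests. Report in the SAP the procedure actually used, how the arm sizes were reached, whether the next assignment was foreseeable, and the numbers per arm and walking category. Label the baseline-adjusted comparison post hoc if outcome data have been seen.

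**Cost.** One paragraph, a list and an analysis sentence, with no extra subject or visit. The research plan form requires IRB approval before any modification takes effect. The list fixes the split only for those allocated. Because item 20 counts completers, dropout can still unbalance the arms: a 7:7 list losing two at random ends 6:6 in 49/91 = 54% of cases, though never 8:4. The plan should say how dropouts are replaced.

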**17. Will radioactive material be administered or will subjects be exposed to ionizing radiation?**

• *Ex. Radiographic equipment, fluoroscopic equipment, and CT scanners, etc.*

No  Yes

**18. In your judgment, could the objectives of the research be met in a way that presents less risk to subjects?**

No  Yes *please explain:*

**Section 4 – Subject Selection, Recruitment, and Vulnerable Populations**

**19. Anticipated duration of entire study reported in years: 2**

20. Estimated number of subjects to be studied at the LSCDVAMC or charts/records to be reviewed.

- Provide answers for ***each cohort*** including normal controls; (patients, family members, treating physicians,):
  - Up to 350 chart/record reviews.
  - Up to 48 subjects with gait deficits from MS will be screened to get 12 subjects to complete the study.

21. Estimated number of subjects to be studied or charts/records to be reviewed at all sites

- Provide answers for ***each cohort*** including normal controls; (patients, family members, treating physicians,)

N/A SINGLE SITE

22. Duration of individual subject participation

Provide answers for ***each cohort*** including normal controls; (patients, family members, treating physicians,). Up to 1 year

Chart/record review  N/A

23. Age range of subjects

- provide answers for ***each cohort***, including normal controls:

Adults 18 years or greater

Specific age range (list age range):

Children –waiver from VACO:  attached  pending- provide submission date:

*\*\*Contact AO/Research [[contact]](mailto:[contact]) for guidance..*

24. Which of the following will be recruited or reviewed for this study (check all that apply)?

Veteran Inpatients

Men

Veteran Outpatients

Women

Veteran Families

\*Normal volunteers

\*Non-Veterans; Provide justification: Non-veterans will be recruited only if not enough veterans are willing to participate. Patients with MS will be recruited by referral from treating physicians who will be informed verbally of the study.

\*According to VHA Handbook 1605.04 Notice of Privacy Practices VHA must provide a copy of its VHA Notice of Privacy Practices to all non-Veteran patients (e.g., active duty personnel or those seeking care in humanitarian circumstances) receiving care or treatment at a VHA health care facility

**25. Which vulnerable population(s) will be TARGETED for recruitment in this study:**

- Indicate only those populations that are specifically targeted for the research described in this document.
- *It is not necessary to check any box if, for example, your study will include a full range of subjects, some of whom may be elderly or subjects who might incidentally be employees.*

- N/A Chart Review (proceed to Item 30)
- NONE (proceed to Item 26)
- Medical students, house staff, or Employees of the VAMC or Case
- Pregnant Women OR Women who are Breastfeeding, Human Fetuses, or Neonates
- Children – Complete Section 14 “Children as Research Subjects”
- Prisoners (The LSCDVAMC does not conduct research involving prisoners)
- Targeting Persons over Age 65
- Persons with Acute/Severe Mental/Physical Disabilities (describe):
- Persons with Cognitive, Social, Economic, or Educational Disadvantages (describe):
- Others (describe):

**a. Provide the Scientific and Ethical reasons for Targeting these vulnerable populations in the research:**

**b. What additional safeguards or provisions will be used to protect the rights and welfare of the identified targeted vulnerable subjects?**

- Surrogate consent
- Subject assent
- Use of a consent or Medical monitor
- Use of a waiting period
- A patient advocate will participate in the informed consent process
- Key elements of informed consent will be presented orally
- No supervisor or rater will be involved in obtaining consent
- Other - Describe Additional safeguards you plan to use:

c. Describe the procedures used to ensure that the subject's legally authorized representative is well informed regarding his/her role and obligation to protect persons with impaired decision making capacity:

26. Procedures for Recruiting Subjects -check all that apply and attach all recruitment materials:

Not Applicable

Materials; Recruitment Letter, Posting on Bulletin Board, Brochure, Flyer, Post card, etc.

Media; Internet Ads, Press Releases, Newspaper, Radio

Investigator's Patient Population

Physician Referral

Letters to Physicians/Clinicians

Other (describe):

27. Will VA computer systems be used to identify potential subjects?

- e.g. VISTA, CPRS, Pharmacy Databases, other clinical databases, etc,

No  Yes- Describe how the computer will be used to identify patients. List all systems used and all information to be collected: The PI will use VISTA, CPRS and the Cleveland SCI/D catchment registry. These systems will be used to generate a list of patients with MS within the SCI Center catchment area. The list will include patient name, etiology of MS, social security number and primary VA care site.

28. Will subjects be identified and/or recruited in clinics and/or inpatient wards at the LSCDVAMC?

No  Yes- explicitly describe your process for identifying and/or recruiting these patients: (address all cohorts): PI is attending physician in neurology and SCI wards treating patients with MS. He will describe this research study to potential volunteers and provide them with contact information for further evaluation for participation in the study.

29. In addition to the consent form will any other materials be given to the subject?

N/A Chart/data review

No  Yes- check all that apply and submit for IRB review:

Letter

Information Sheets

Questionnaire, Survey, Diary

Other (flyer, brochure, describe):

30. Please list by bullet point inclusion/exclusion criteria for the study.

- *Entry criteria should be as detailed as necessary to define the subject population(s) under study and reduce confounding design. Include precise criteria for age, gender, and other relevant factors.*
- *List specific exclusion criteria which could interfere with the study design or place a subject at risk during the study.*
- *Provide answers for each cohort, including normal controls.*

Suitable candidates will be identified via chart reviews before undergoing the consent process and evaluation.

